5 STUDY ENROLLMENT AND WITHDRAWAL

5.1 Study Population

184 women with WHO class II anovulation/PCOS actively seeking pregnancy (or 92 per each treatment arm) aged \geq 18 to \leq 40 years will be randomized. The overall goal of enrollment criteria is to identify a population of healthy women with anovulatory or oligo-ovulation (WHO Class II anovulation) and infertility not specified by another cause. Infertility will be determined by clinical history. PCOS will be determined by including two of three findings: oligo- or anovulation, hyperandrogenism or polycystic ovaries on ultrasound. Definitions are from the 2018 Recommendations from the international evidence-based guideline for the assessment and management of polycystic ovary management(3).

- Oligo-ovulation: cycles less than 21 days or greater than 35 days or less than 8 cycles per year
 - Ovulatory dysfunction/Anovulation: women with regular cycles with anovulatory progesterone or with amenorrhea
- Polycystic ovarian morphology (PCOM) on ultrasonography: follicle number (measuring 2-9 mm) per ovary of ≥ 20 and/or ovarian volume >10 ml on either ovary, ensuring no corpora lutea, cysts or dominant follicles are present if using volume only.
- Hyperandrogenism: determined by evidence of clinical or biochemical hyperandrogenism
 - o Clinical: symptoms and signs of hirsutism, acne or alopecia
 - Biochemical: elevations in calculated free testosterone or free androgen index (Total Testosterone level divided by SHBG level and multiply by 100). Levels should not have been assessed while on combined hormonal contraceptive
- If PCOS criteria is not met, normogonadotropic anovulation should be met with confirmation of anovulation/olig-ovulation and normal FSH and estradiol levels.
- Infertility: Inability of couple to achieve successful pregnancy after 12 months of regular timed unprotected intercourse in women less than 35 years of age; and after 6 months of regular intercourse without use of contraception in women 35 years and older(20). If in the clinical case of anovulation/oligo-ovulation, 12 month period of time "infertility" is not necessary.

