trial of letrozole alone versus combination of letrozole and clomiphene citrate (CC) for up to 3 treatment cycles. Letrozole dosing will be increased in a stair-step fashion based on ovulation results. Participants will return for a mid-luteal ultrasound and progesterone lab to determine ovulatory status. Women will be randomized in a 1:1 ratio and the randomization scheme will be coordinated through the UIHC. Randomization will be stratified by site, age and BMI. The primary analysis will use an intent-to-treat approach to evaluate ovulatory rate in the

two treatment arms.

Objectives: To determine efficacy and safety of the combination letrozole and CC compared to letrozole alone in achieving ovulation in

infertile women with anovulation.

Primary Outcome: Ovulation will be the primary outcome determined by a mid-luteal progesterone level ≥ 3 and cumulative ovulation rate will be the primary efficacy parameter.

Secondary Outcome: Secondary efficacy parameters will include pregnancy rate (conception and clinical pregnancy), live birth rate, multiple gestation live birth rate, pregnancy loss rate (biochemical, miscarriage, ectopic) and time to pregnancy.

Side effect profile and complication rate will be monitored and reported.

Obstetric outcomes will include pregnancy complication rate, birth weight and sex, neonatal complication rate.

Ultrasound findings will be reported and compared between the two groups including: number of corpora lutea and endometrial thickness.

ClinicalTrials.gov Identifier

201906826

Population: 184 healthy women infertile women with polycystic ovary

syndrome or normogonadotropic normoestrogenic anovulation or oligo-ovulation, age \geq 18 to \leq 40. Additionally, the couple will

have no other major infertility factor.

Phase: IV

Number of Sites: 4 sites

University of Iowa Hospitals and Clinics Iowa City, IA with 2 ancillary sites

- Quad Cities Clinic, Davenport, IA
- Jordan Creek Clinic, Des Moines, IA

University of Wisconsin, Generations Clinic, Middleton, WI

Description Intervention:

of 184 women will be equally randomized to two different treatment arms at time of menses (spontaneous or induced with progestin withdrawal) or random start: A) letrozole 2.5 mg every day for 5 days (days 3-7 of cycle), or B) letrozole 2.5 mg and clomiphene citrate 50 mg every day for 5 days (days 3-7 of cycle), for a total of up to 3 treatment cycles.

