3.1.1 Primary Outcome Measure

The primary outcome measure is the occurrence of ovulation during the study period. Ovulation is defined as a mid-luteal progesterone level > 3 ng/mL. This will be tested 6-8 days following the patient reporting of an LH surge. If no LH surge is detected the lab will be drawn on cycle day 21-24. We will also analyze the ovulation rate of the follow up progesterone level.

We will utilize an intent-to-treat approach for the primary analysis of ovulation rate (utilizing the first progesterone level of each cycle) within the two treatment arms. If it is determined that timing of the initial progesterone level is inaccurate based on LH testing or patient symptoms, the progesterone test that is most clinically in line with accurate timing (6-8 days post LH surge) will be used. Ovulation rate will also be reported in those with a delayed response to treatment (needed repeat progesterone level due to anovulatory mid-luteal P4 level and follicle ≥ 14 mm). Patients will be analyzed according to the treatment group to which they are assigned, even if they did not receive the intended treatment or received only a portion of it. We will also perform a per protocol analysis to include only those patients who initiate treatment. Thus, those that are randomized but do not take the treatment due ineligibility will be excluded from the per protocol analysis. This per protocol analysis will provide data that is helpful to clinicians as it will include only those who initiated treatment.

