5.2 Subject Inclusion Criteria

In order to be eligible to participate in this study, an individual must meet all of the following criteria:

- 1. Diagnosis of infertility (described above)
- 2. Normogonadotropic normoestrogenic (WHO Group II) anovulation or oligo-ovulation:
 - Diagnosis of PCOS as described above OR
 - b. Self-reported menstrual cycle length < 21 or > 35 days or < 8 cycles per year. For women with variable cycle length not consistently <21 days or >35 days, a serum progesterone between day 21 and 35,
 <3 ng/ml will be considered evidence of oligo-ovulation AND normal estrogen level and FSH level
- 3. Age 18-40
- 4. BMI < 50
- 5. Normal semen analysis in past two years according to World Health Organization cut off points (concentration and motility) or a total motile sperm count greater than 10 million. Morphology results will not affect eligibility. If male partner has fathered a child, SFA is not necessary.
- 6. Desire to achieve a pregnancy
- 7. Willing to comply with study procedures for the duration of the study.

 Ability to have intercourse at least twice weekly and follow study protocol

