8 STUDY PROCEDURES /EVALUATIONS

8.1 Study Procedures/Evaluations

- Medical history will be assessed by chart abstraction and confirmation with the patient at the Screening or Enrollment visit.
- Physical examination will include chart abstraction of height and weight and BMI and if not in chart will be performed at screening visit.
- Participants will be asked about hirsutism symptoms.
- Transvaginal ultrasound of uterus and ovaries will be performed to obtain the following measures: endometrial thickness and evaluation for presence of corpora lutea and number of corpora lutea.
- Urine pregnancy tests
- Participant Journal Logs will be used to track medication adherence, side effects, intercourse, and concomitant medications

Standard Clinical care:

- Transvaginal ultrasound will also be performed at the ongoing pregnancy visit to record the number of gestational sacs, measurement of gestational sac(s), yolk sac(s), crown rump length, presence of fetal heart motion and rate and any abnormalities.
- Assessment of tubal factor and uterine cavity by saline sonohystogram, hysterosalpingogram, or laparoscopy if recommended by provider however not required to participate in the study
- Semen analysis of male partner to rule out male factor
- 8.2 Medical record review will be performed for labs, including: TSH, prolactin, HbgA1c, 17-OH Progesterone, AMH, Rubella, FSH and estradiol, Total testosterone and SHBG; progesterone documenting anovulation. All of these labs are not required for participation but if they have been done should be documented. Documentation of TSH, HbgA1c and Rubella status recommended for participation. These will be entered into RedCap.

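### Inclusion criterion 2 contradicts itself: its heading requires anovulation or oligo-ovulation, but sub-item 2a, read literally, can be met without either

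*Combined protocol and SAP*

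**What the plan says.** The protocol describes its target population in one way and tests for it in another.

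- **Intent.** In section 5.2 the heading of inclusion criterion 2 reads "Normogonadotropic normoestrogenic (WHO Group II) anovulation or oligo-ovulation". The enrolment goal in 5.1, the primary hypothesis in 3.1 and the trial title also describe women with anovulation or oligo-ovulation.
- **Operative rule.** Sub-item 2a under that heading reads "Diagnosis of PCOS as described above OR", and the cycle-length and progesterone evidence sits only in 2b. The definition that 2a points to is in 5.1: "PCOS will be determined by including two of three findings: oligo- or anovulation, hyperandrogenism or polycystic ovaries on ultrasound". Any two findings suffice, so ovulatory disturbance need not be one of them.
- **When anovulation is confirmed.** Section 5.1 asks for it only in the other branch: "If PCOS criteria is not met, normogonadotropic anovulation should be met with confirmation of anovulation/olig-ovulation and normal FSH and estradiol levels".
- **Baseline.** Section 4.2 requires an anovulatory progesterone for a random start. For a start with menses it requires only a negative pregnancy test.
- **Exclusions.** Nothing in section 5.3 removes a woman with PCOS who ovulates.
- **Endpoint.** Section 3.1.1: "The primary outcome measure is the occurrence of ovulation during the study period". The Protocol Summary and section 12.2 treat it as cumulative over up to three cycles.

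**The concern.** Eligibility and endpoint concern the same event. A woman who already ovulates without treatment is likely to have at least one progesterone result above the cut-off in up to three cycles, whichever arm she is in. She then says little about whether adding clomiphene helps. She raises the ovulation rate in both arms, pulls the absolute difference towards zero, and makes the result less descriptive of the anovulatory women named in the title and hypothesis. Sites reading the heading and sites reading 2a could also enrol different populations.

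**Working it through.** **Step 1: trace one woman through the rules.** Take clinical hyperandrogenism, polycystic ovaries by follicle count, and ovulatory cycles.

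- PCOS definition (5.1): two of three findings, so met.
- Criterion 2a: met by that diagnosis. 2b is not needed because the two are joined by OR.
- Confirmation of anovulation (5.1): not triggered, because PCOS criteria are met.
- Infertility (5.1): she must satisfy the duration rule of 12 months, or 6 months from age 35. The waiver applies only to anovulation or oligo-ovulation.
- Baseline (4.2): with a start on cycle day 1-3, no progesterone is required.
- Exclusions (5.3): none applies.
- Criterion 2 heading: **not** met.

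The heading is the only line that stops her, and the sub-item beneath it does not test for what the heading says.

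**Step 2: reproduce the planned sample size.** Section 12.1.4 gives 80% power, a 20-point absolute difference, 10% dropout and 92 per arm. Section 12.2 gives a two-sided chi-square test at 0.05. No arm rates are stated. Assume 60% v 80%, with mean 0.70:

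n = [1.96·√(2·0.70·0.30) + 0.8416·√(0.60·0.40 + 0.80·0.20)]² / 0.20² = (1.270 + 0.532)² / 0.04 ≈ 81.2, so 82 per arm. Then 82/0.9 = 91.1, so 92 per arm and 184 in total.

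This matches the plan, and power at 82 per arm is 80.4%. The 60% remains an assumption. The prior-trial table in 12.1.1 pools to (178 + 204 + 179)/(360 + 318 + 268) = 561/946 = 59.3%. That is a per-cycle figure, so it may explain a 60% planning rate but does not establish it as a cumulative one.

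**Step 3: dilution.** Let a share f of women ovulate with the same probability r in both arms:

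- letrozole: p1 = (1 − f)·0.60 + f·r
- combination: p2 = (1 − f)·0.80 + f·r
- difference: p2 − p1 = 0.20·(1 − f)
- power = Φ{[(p2 − p1)·√n − 1.96·√(2p̄(1 − p̄))] / √(p1(1 − p1) + p2(1 − p2))}

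Example with f = 10%, r = 1 and n = 82: rates are 64% v 82%, and power = Φ[(0.18·9.055 − 1.96·0.628)/0.615] = Φ(0.65) = 74.2%.

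| Share f | Difference (points) | Power, n = 82, r = 1.0 | Power, n = 82, r = 0.9 | Power, n = 92, r = 1.0 |
|---|---|---|---|---|
| 0% | 20 | 80.4% | 80.4% | 84.7% |
| 5% | 19 | 77.4% | 77.0% | 82.0% |
| 10% | 18 | 74.2% | 73.2% | 79.0% |
| 20% | 16 | 67.2% | 64.9% | 72.3% |

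The n = 92 column applies if every randomised woman contributes an outcome at these rates. Holding 80% power after 10% dropout (r = 1.0) would need totals of 196, 212 and 248 at shares of 5%, 10% and 20%.

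**Step 4: type I error.** If clomiphene adds nothing, p1 = p2 for every f and r, because randomisation gives both arms the same expected mix. The false-positive rate is not raised.

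**The case against.** The strongest reply is that criterion 2 already excludes these women. Section 5.2 requires every criterion to be met, criterion 2 is anovulation or oligo-ovulation, and 2a sits under it. Section 4.1 equates WHO class II anovulation with women with PCOS, so the authors may use PCOS as shorthand for anovulatory PCOS. This stands as evidence of intent. It does not close the gap, because 2a and the 5.1 confirmation sentence are the tests supplied for the heading, and neither enforces it. The Population line of the Protocol Summary even lists PCOS as an alternative to anovulation.

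A reader might infer more than the documents support:

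- **That ovulatory women are in fact being enrolled because 2a is what sites check.** The REDCap eligibility form is not in the documents, so how sites apply criterion 2 is unknown.
- **That section 8.2 waives proof of anovulation**, since it says "All of these labs are not required for participation but if they have been done should be documented". That is a general chart-abstraction line covering many tests. It cannot override 2b, where a progesterone result is the evidence for women with variable cycles.
- **That every woman entering on hyperandrogenism plus polycystic ovaries ovulates.** Section 5.1 recognises regular cycles with an anovulatory progesterone. It also requires a scan free of corpora lutea, cysts and dominant follicles when morphology rests on volume alone, which narrows that route for a cycling woman.
- **That the trial is underpowered by a known amount.** The share is not given, and the duration rule may keep it small. The prior trial and the pilot behind the planning may themselves have included ovulatory PCOS, in which case the planned difference already contains some dilution.

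The protocol also takes its PCOS definitions from a cited guideline, so admitting ovulatory PCOS could be deliberate. If so, the heading, goal and hypothesis are the lines out of step, and the choice needs a justification.

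**Conclusion.** The point holds as an internal contradiction that needs reconciling. The heading of criterion 2, the 5.1 goal and the hypothesis require ovulatory disturbance; 2a and the 5.1 confirmation sentence do not. The literal rule leaves room for women near the ceiling of the primary endpoint. The consequence is a smaller absolute difference and a less applicable result, not a false-positive risk.

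The size cannot be derived from the documents. The power figures in the table rest on an unstated 60% v 80%, an assumed 90-100% ovulation in both arms among ovulatory women, and an unknown share. At a 5% share the loss is about 3 points. With 82 evaluable per arm the design starts at about 80%, so it has little slack on these assumptions. The correction is worth making because it is cheap and brings the rule into line with the trial's own title.

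**What to change.** 1. Reconcile 2a and the PCOS sentence in 5.1 with the criterion 2 heading by stating that oligo- or anovulation, as 5.1 already defines it, must be one of the two qualifying findings.
2. Add a REDCap eligibility field recording which findings qualified each woman.
3. Pre-specify a sensitivity analysis of the primary outcome that leaves out any already-randomised woman who qualified without ovulatory disturbance. Classify her from records that predate randomisation. The exclusion then depends only on a baseline characteristic, and the randomised comparison is preserved among those who remain.

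The cost is a short amendment, one extra eligibility field, one extra analysis and slightly slower recruitment from the loss of some otherwise eligible women.

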5.2 Subject Inclusion Criteria

In order to be eligible to participate in this study, an individual must meet all of the following criteria:

- 1. Diagnosis of infertility (described above)
- 2. Normogonadotropic normoestrogenic (WHO Group II) anovulation or oligo-ovulation:
 - Diagnosis of PCOS as described above OR
 - b. Self-reported menstrual cycle length < 21 or > 35 days or < 8 cycles per year. For women with variable cycle length not consistently <21 days or >35 days, a serum progesterone between day 21 and 35,
 <3 ng/ml will be considered evidence of oligo-ovulation AND normal estrogen level and FSH level
- 3. Age 18-40
- 4. BMI < 50
- 5. Normal semen analysis in past two years according to World Health Organization cut off points (concentration and motility) or a total motile sperm count greater than 10 million. Morphology results will not affect eligibility. If male partner has fathered a child, SFA is not necessary.
- 6. Desire to achieve a pregnancy
- 7. Willing to comply with study procedures for the duration of the study.

 Ability to have intercourse at least twice weekly and follow study protocol

5.3 Subject Exclusion Criteria

An individual who meets any of the following criteria will be excluded from participation in this study:

- 1. Current pregnancy
- 2. Current use of oral contraceptives, injectable contraceptives, implanted hormonal contraceptives, or oral, vaginal or transdermal estrogens or progestins. 1-month washout required, 3 months for injectable/implanted progestin contraceptives.
- Patients with other known cause of infertility: endometriosis, tubal factor, diminished ovarian reserve (defined as AMH < 1 or AFC < 10), uterine abnormalities.
 - a. Patients with unilateral tubal patency can be enrolled, provided at least one tube is open.
 - b. Patients with mild endometriosis can be enrolled
- 4. Uncontrolled thyroid disease (normal TSH in past 3 years is adequate).

- a. Patients with uncorrected thyroid disease defined based on their local lab or at UIHC (0.27 to 4.20 µIU/mL). Once corrected and within this range, they may be enrolled if the other inclusion and exclusion criteria are met. A normal lab within the last 3 years is adequate for entry
- 5. Hyperprolactinemia (prolactin > 30 ng/dl x 2). A normal prolactin within the past year at local lab or at UIHC (4.8 to 23.3 ng/mL) is adequate for entry if history of hyperprolactinemia.
- 6. Medical conditions in which we recommend avoiding pregnancy until under improved control
 - a. Patients with poorly controlled Type 1 or Type 2 diabetes (defined as a hemoglobin A1c > 6.5-7.0%)
 - b. Uncontrolled hypertension (medicated or unmedicated, BP >160/100 x 2)
 - c. Bariatric surgery within the past year
 - d. Untreated endometrial hyperplasia
 - e. Current alcohol use > 14 drinks per week
- 7. Patients with contraindications to clomiphene citrate: hypersensitivity to CC or any of its components, history of liver disease or known liver disease (LFT's are not necessary prior CC use and enrollment into the study), unknown cause of abnormal uterine bleeding, intracranial lesion.
- 8. Patients with contraindications to letrozole: hypersensitivity to letrozole or any of its components.
- 9. Patients taking medications known to affect reproductive function or metabolism or that are an absolute contraindication during pregnancy.
 - a. Patients taking Metformin can be enrolled, provided they have documented impaired glucose tolerance or insulin resistance.
 Patients who are not taking Metformin for these indications will be excluded.
- 10. If patients are suspected based on clinical findings for other etiologies that mimic PCOS, work up must be completed to exclude other etiologies prior to enrollment (i.e. Cushing's syndrome, androgen-secreting tumor).
- 11. Prior diagnosis of congenital adrenal hyperplasia or Cushing's Disease or Syndrome

5.4 Strategies for Recruitment and Retention

Strategies for Recruitment

Potential study participants will be recruited from couples seeking fertility evaluation and/or ovulation induction at participating fertility clinics and other referring practices providing reproductive care. Study team members will review clinic schedules for their

center and will be approached regarding the study by their clinician, a study coordinator, or another member of the research team while at the clinic for their initial consult or clinical visit. Couples will be given information about the study, offered pre-screening to assess eligibility, and given the opportunity to schedule an enrollment visit.

Study information materials and contact information will be provided to outside and community clinics that commonly refer patients to participating study centers. A study coordinator or another member of the research team will review study information and assess eligibility with couples referred to the study from external clinics, clinicaltrials.gov, word of mouth, or other external sources.

Recruitment at UW- Recruitment will occur in the clinical setting through posters, brochures, digital posters displayed at UW Health Clinics, and referral in both the Department of Obstetrics and Gynecology and the UW Health Generations Fertility Clinic through conferencing software. If a patient hears about the study from a referring provider or someone not on the research team, the referring provider will direct the patient to contact the research team if they are interested in participating or hearing more about the study. The referring provider will provide recruitment materials so that the patient can contact the team directly.

Recruitment strategies for individual sites have been approved by local IRBs.

Strategies for Retention

Study coverage of ovulation induction medication and ultrasounds are expected to be sufficient incentive for participation in the study. Additional measures to retain subjects for up to three cycles of ovulation induction will involve establishment of positive rapport between the study team and participants, appointment and scheduling reminders, and regular communication regarding ultrasound and lab results.

Participants will be given the opportunity to schedule future study visits during the preceding study visit or any time prior to the study visit. Participants will receive an appointment reminder within the week prior to their scheduled appointment. Study staff will utilize a system of reminder emails and phone calls to contact participants who need to schedule their next study visit of if a study visit is missed.

Retention strategies for pregnancy outcome data will involve obtaining consent to release information forms at participant enrollment visits, and study team confirmation of the participant's planned obstetric care provider when pregnancy is detected. In the event that an updated consent to release information form is not on file post-delivery,

study staff will utilize a system of reminder emails, phone calls, and mailed correspondence to obtain an up-to-date form. This system will involve an initial email and two mailed letters with request for completion of forms, with each email request and mailed letter request followed by two phone calls in the case of participant non-response.

Consent to obtain information forms for infants born during study follow up will be obtained following delivery.

At the University of Iowa- Study staff will utilize a follow up system of reminder emails, phone calls, and mailed correspondence to obtain parental consent to release information for infants. This system will involve an initial email and two mailed letters with request for completion of forms, with each email request and mailed letter request followed by two phone calls in the case of participant non-response.

At the University of Wisconsin- At the time of consent, the subject will sign a consent form that includes consent to obtain information from the newborn's medical record. A release of information form to obtain information for neonates born during study follow up will be obtained when the subject becomes pregnant. Study staff will have these forms explained and completed at a standard clinical visit or virtually

